9.2.3. Adverse Event Summaries

An overall summary of AEs by treatment group will include the following:

- Number (%) of participants who had any TEAEs
- Number (%) of participants who had any serious TEAEs
- Number (%) of participants who had any Grade 3 or higher TEAEs
- Number (%) of participants who had any TEAEs related to parsaclisib
- Number (%) of participants who had any TEAEs related to ruxolitinib
- Number (%) of participants who temporarily interrupted parsaclisib because of TEAEs
- Number (%) of participants who temporarily interrupted ruxolitinib because of TEAEs
- Number (%) of participants who permanently discontinued parsaclisib because of TEAEs
- Number (%) of participants who permanently discontinued ruxolitinib because of TEAEs
- Number (%) of participants who had parsaclisib dose reductions because of TEAEs
- Number (%) of participants who had ruxolitinib dose reductions because of TEAEs
- Number (%) of participants who had any fatal TEAEs

The following summaries will be produced by MedDRA term (if 10 or fewer participants appear in a table, a listing may be appropriate):

- Summary of TEAEs by MedDRA SOC and PT
- Summary of TEAEs by MedDRA PT in decreasing order of frequency
- Summary of TEAEs by MedDRA SOC, PT, and CTCAE grade category
- Summary of Grade 3 or higher TEAEs by MedDRA SOC and PT
- Summary of Grade 3 or higher TEAEs by MedDRA PT in decreasing order of frequency
- Summary of serious TEAEs by MedDRA SOC and PT
- Summary of serious TEAEs by MedDRA PT in decreasing order of frequency
- Summary of parsaclisib treatment-related TEAEs by MedDRA SOC and PT

- Summary of ruxolitinib treatment-related TEAEs by MedDRA SOC and PT
- Summary of parsaclisib treatment-related TEAEs by MedDRA PT in decreasing order of frequency
- Summary of ruxolitinib treatment-related TEAEs by MedDRA PT in decreasing order of frequency
- Summary of parsaclisib treatment-related TEAEs by MedDRA SOC, PT, and CTCAE grade category
- Summary of ruxolitinib treatment-related TEAEs by MedDRA SOC, PT, and CTCAE grade category
- Summary of Grade 3 or higher parsaclisib treatment-related TEAEs by MedDRA SOC and PT
- Summary of Grade 3 or higher ruxolitinib treatment-related TEAEs by MedDRA SOC and PT
- Summary of parsaclisib treatment-related serious TEAEs by MedDRA SOC and PT
- Summary of ruxolitinib treatment-related serious TEAEs by MedDRA SOC and PT
- Summary of TEAEs with a fatal outcome by MedDRA SOC and PT
- Summary of TEAEs leading to parsaclisib dose reduction by MedDRA SOC and PT
- Summary of TEAEs leading to ruxolitinib dose reduction by MedDRA SOC and PT
- Summary of TEAEs leading to parsaclisib dose interruption by MedDRA SOC and PT
- Summary of TEAEs leading to ruxolitinib dose interruption by MedDRA SOC and PT
- Summary of TEAEs leading to discontinuation of parsaclisib by MedDRA SOC and PT
- Summary of TEAEs leading to discontinuation of ruxolitinib by MedDRA SOC and PT
- Summary of TEAEs by MedDRA PT: life-table method
- Summary of TEAEs by MedDRA SOC and PT: life-table method
- Summary of treatment-emergent AESIs by MedDRA PT
- Median time to the first onset of treatment-emergent AESIs by MedDRA PT
- Median longest duration of treatment-emergent AESIs by MedDRA PT

9.3. Clinical Laboratory Tests

9.3.1. Laboratory Value Definitions

Laboratory values and change from baseline values will be summarized descriptively by visit. Baseline will be determined according to Section 4.1.4. If there are multiple values that meet the criteria for baseline, additional rules may be provided after consultation with the medical monitor to delineate which value will be defined as baseline.

Laboratory test values will be assessed for severity based on the numerical component of CTCAE v5.

9.3.2. Laboratory Value Summaries

All test results and associated normal ranges from central laboratories will be reported in SI units. Any laboratory test results and associated normal ranges from local laboratories will be converted to SI units.

When there are multiple nonmissing laboratory values for a participant's particular test at a scheduled visit, central laboratory values have higher priority over local laboratory values. If a tie still exists, the laboratory value with the smallest laboratory sequence number will be used in by-visit summaries.

Numeric laboratory values will be summarized descriptively in SI units, and non-numeric test values will be tabulated when necessary. In addition, box-and-whisker plots will be provided for HGB, platelet counts, leukocytes, and neutrophils.

A table for number of participants with abnormal ALT, AST, bilirubin, and creatinine will be tabulated by treatment group.

For test results that will be summarized with available normal ranges, the number and percentage of participants with laboratory values being low (but never high), normal, high (but never low), and both low and high will be calculated for each test. This shift summary will be produced for each test for the safety population. The denominator for the percentage calculation will use the number of participants in the baseline category (ie, low, high, normal, missing) as the denominator for the percentage in each of the categories during the study.

Severity grades will be assigned to laboratory test values based on the numerical component of CTCAE v5. Shift tables will be presented showing change in CTCAE grade from baseline to worst grade postbaseline. Separate summaries for abnormally high and abnormally low laboratory values will be provided when the laboratory parameter has both high and low grading criteria. The denominator for the percentage calculation will be the number of participants in the baseline category. The number of participants who experienced worsening of laboratory abnormalities will be summarized by maximum severity.

In cases where differentials of hematology parameters are obtained without corresponding absolute count data, efforts will be made to investigate if the conversion to an absolute value will lead to additional abnormalities. This will be discussed with the clinical team regarding appropriate documentation and action.

9.3.3. Potential Hy's Law Events

Participants with elevated ALT or AST $> 3 \times$ ULN range and alkaline phosphatase $< 2 \times$ ULN range accompanied by total bilirubin $> 2 \times$ ULN range at the same visit will be listed by treatment group.

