Contact IXRS	X	X	
Review criteria for crossover	X		
Concomitant medications	X	X	
Dispense parsaclisib and ruxolitinib	X	X	
Distribute reminder cards	X	X	
Collect study drug and reference treatment and review diary cards	X*	X†	*Parsaclisib/matching placebo and ruxolitinib bottles/blister packs to be collected. †Parsaclisib and ruxolitinib bottles/blister packs to be collected.
Transfusion history status	X	X	
Safety assessments			
Record AEs	X	X	Body systems with symptoms should be physically examined.
PJP	X	X	Prophylaxis continues from crossover visit through at least 2-6 months beyond the last dose of study treatment..
Efficacy assessments			
Spleen palpation	X	X	
Dispense and/or bring MFSAF v4.0 diary to visit	X	X	Diary continues only for early crossover before Week 24 and ends at Week 24.
MFSAF v4.0 diary	X	X	Diary continues only for early crossover before Week 24 and ends at Week 24.
ECOG performance status			
Laboratory assessments			
Serum chemistry	X	X	Then follow Table 5 .
Hematology	X	X	Then follow Table 5 .

Table 5: Schedule of Laboratory Assessments for All Participants

[figure not shown]
	Screening	Baseline	Day 1	End of Weeks 2, 6, 10, and 30 and Then Q12W	End of Weeks 4, 8, 12, 16, 20, and 24 and Then Q12W	EOT or Early Termination Visit	Safety Follow-Up 30-35 Days After Last Dose of Parsaclisib	Notes
Window				The window for laboratory-only visits is ± 3 days through Week 10 inclusive, and ± 7 days for laboratory-only visits beginning at Week 30 and Q12W				
Local laboratory assessments								
Serum chemistry	X	X*			X	X	X	*Should be collected as close as possible to Day 1 but may be drawn up to 3 days before first dose. Only 1 sample for baseline/Day 1 is required.
Hematology	X	X*		X	X	X	X	*Sample should be collected as close as possible to Day 1 but may be drawn up to 3 days before first dose. Only 1 sample for baseline/Day 1 is required. Note that if platelet count is $< 50 \times 10^9/L$ at baseline, the platelet count at screening will be used for stratification/randomization. See Section 8.1.3.
Coagulation panel	X				X*	X	X	*Required at Weeks 12 and 24 and Q12W thereafter.
Urine pregnancy test		X			X*	X*		All female participants of childbearing potential. *Pregnancy tests should be repeated if required by local regulations.

Table 5: Schedule of Laboratory Assessments for All Participants (Continued)

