2.6.1.3. Potential Risks of PI3K Inhibition Based on Other Agents in Class

Idelalisib was approved by the FDA in July 2014 for treatment of relapsed/refractory follicular lymphoma and relapsed small lymphocytic lymphoma and for treatment of chronic lymphocytic leukemia in combination with rituximab. Severe toxicities seen with the use of this agent include hepatotoxicity (fatal and/or serious occurring in 16%-18%), fatal and/or serious diarrhea or colitis (14%-20%), intestinal perforation, pneumonitis, and infections (fatal and/or serious occurring in 21%-48%). PJP infection and CMV infection have also been reported ([Zydelig® 2018](#)).

Copanlisib was approved in 2017 for the treatment of relapsed follicular lymphoma. Clinically important toxicities observed with this agent include SAEs, including fatal infections (19%), usually pneumonia, Grade 3 or 4 hyperglycemia (41%), and Grade 3 hypertension (26%). Serious PJP occurred in 0.6% of patients treated with copanlisib ([Aliqopa® 2019](#)).

Duvelisib was approved in 2019 for the treatment of relapsed or refractory chronic lymphocytic leukemia, small lymphocytic lymphoma, or follicular lymphoma. Clinically important toxicities observed with this agent include fatal and/or serious infections (31%), fatal and/or serious diarrhea or colitis (18%), fatal and/or serious cutaneous reactions (5%), or fatal and/or serious pneumonitis (5%). Serious, including fatal PJP occurred in 1% of patients taking duvelisib, and CMV reactivation also occurred in 1% of patients taking duvelisib ([Copiktra® 2019](#)).

Participants in the present study will be monitored closely for the development of bacterial, fungal, or viral infections and will have treatment interrupted and dose reduced as appropriate. Participants will receive prophylaxis for PJP and will be monitored for CMV viremia during the study.

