5.2. Exclusion Criteria

Participants are excluded from the study if any of the following criteria apply:

1. Prior use of any JAK inhibitor.
2. Prior therapy with any drug that inhibits PI3K (examples of drugs targeting this pathway include but are not limited to INCB040093, idelalisib, duvelisib, buparlisib, copanlisib, and umbralisib).
3. Use of experimental drug therapy for MF or any other standard drug (except hydroxyurea) used for MF or another indication within 3 months of starting study drug and/or lack of recovery from all toxicities from previous therapy to \leq Grade 1. Hydroxyurea used for MF or another indication must be discontinued 3 weeks prior to starting study drugs (Day 1).
4. Inability to swallow food or any condition of the upper gastrointestinal tract that precludes administration of oral medications.

5. Recent history of inadequate bone marrow reserve; examples include but are not limited to the following:
 - a. Platelet count $< 50 \times 10^9/L$ in the 4 weeks before screening or at the screening laboratory assessment; or platelet transfusion(s) within 8 weeks before screening.
 - b. Absolute neutrophil count $< 0.5 \times 10^9/L$ in the 4 weeks before screening or at the screening laboratory assessment.
 - c. Peripheral blood blast count of $\geq 10\%$ at the screening hematology assessment.
6. Inadequate liver function at screening visit, as demonstrated by the following:
 - a. Total bilirubin $> 2.0 \times ULN$. Note: if total bilirubin is $> 2.0 \times ULN$, the participant may enroll if the direct bilirubin is $< 2.0 \times ULN$.
 - b. ALT or AST $> 2.5 \times ULN$.
7. Inadequate renal function at screening, as demonstrated by creatinine clearance ≤ 50 mL/min estimated based on Cockcroft-Gault formula. The cutoffs for mild, moderate, and severe renal insufficiency based on the Cockcroft-Gault formula are 60 to 90 mL/min, 30 to 59 mL/min, and 0 to 29 mL/min, respectively. If the investigator prefers, he/she may use measured creatinine clearance instead of estimated.
8. Active bacterial, fungal, parasitic, or viral infection that requires therapy. Participants with acute infections requiring treatment should delay screening/enrollment until the course of therapy has been completed and the event is considered resolved. Prophylactic antibiotics or antivirals will be permitted.

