6.7.2. Dose Decreases of Parsaclisib/Placebo for Toxicity

Parsaclisib or matching placebo should be interrupted/decreased first, with no change to the ruxolitinib dosage. Adjustments to ruxolitinib may be utilized if interruption/dose adjustment of parsaclisib or matching placebo does not lead to resolution or at least improvement of the AE within a 14-day period (see Section 6.7.7). Treatment with parsaclisib or matching placebo may be delayed up to 2 weeks (14 days) to allow for resolution of toxicity. Participants may resume

treatment if no medical condition or other circumstance exists that, in the opinion of the investigator, would make the participant unsuitable for further participation in the study. The treating investigator should contact the sponsor to discuss the case of any participant whose treatment has been delayed for more than 14 days before restarting treatment with piasclisib or matching placebo and/or ruxolitinib. Adverse events that have a clear alternative explanation or transient (≤ 72 hours) abnormal laboratory values without associated clinically significant signs or symptoms may be exempt from dose-reduction rules.

Table 11 shows dose-reduction and interruption guidelines for piasclisib and matching placebo. Because participants may enter the study with extensive pretreatment and/or severe bone marrow infiltration by the primary disease, these dose-reduction rules are provided as guidelines (see **Table 11**). **Individual decisions regarding dose reduction/interruption should be made using investigator clinical judgment and in consultation with the sponsor's medical monitor in those cases where the guidelines will not be followed, taking into account relatedness of the AE to piasclisib and the participant's underlying condition.** Available dose strengths for piasclisib/matching placebo are shown in **Table 12**.

Table 11: Guidelines for Interruption and Restarting of Piasclisib/Matching Placebo

Adverse Event	Action Taken
Chemistry	

 • AST and/or ALT $> 5.0 \times$ ULN (Grade 3). 	
Step 1: Interrupt piasclisib or matching placebo for up to 2 weeks (14 days) until the toxicity has resolved to \leq Grade 1 except by approval of the medical monitor.
 
Step 2: Restart piasclisib or matching placebo at the same dose. If assessed as related to piasclisib or matching placebo, restart piasclisib or matching placebo at the next lower dose; monitor as clinically indicated.

Hematology	

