8.3.5. Laboratory Assessments

See [Table 5](#) for the schedule of laboratory assessments and [Table 14](#) for the laboratory tests that will be performed. All Protocol-required laboratory assessments must be conducted in accordance with the Laboratory Manual and the SoA. Information regarding collection, processing, and shipping of laboratory assessments for the central laboratory is provided in the Laboratory Manual.

Clinically significant abnormal laboratory findings are those that are not associated with the underlying disease, unless judged by the investigator to be more severe than expected for the participant's condition. All laboratory tests with values considered clinically significantly abnormal during participation in the study or within 30 days after the last dose of study treatment should be repeated until the values return to normal or baseline or are no longer considered clinically significant by the investigator or medical monitor.

See [Section 9.1](#) for information regarding laboratory abnormalities that should be recorded as an AE in the eCRF. Additionally, if laboratory values from laboratory assessments performed at the institution's local laboratory require a change in participant management (eg, require treatment) or are considered clinically significant by the investigator, then the result(s) of the **specific laboratory assessment(s)** must be recorded in the eCRF.

Blood samples for hematology and serum chemistry analysis for baseline should be taken as close as possible to Day 1 but may be drawn up to 3 days before the first dose of parsaclisib. This blood sample will serve as the pre-parsaclisib baseline sample; a Day 1 sample is not required as long as the baseline sample is obtained within 3 days of the first dose of parsaclisib.

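### The Hy's law listing needs ALT/AST and bilirubin above threshold at one visit, so participants who cross the two thresholds only at different visits are left out of it

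*SAP*

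**What the plan says.** SAP 9.3.3 defines the listing in one sentence. It starts from "Participants with elevated ALT or AST $> 3 \times$ ULN range and alkaline phosphatase $< 2 \times$ ULN range" and continues "accompanied by total bilirubin $> 2 \times$ ULN range at the same visit will be listed by treatment group". It gives no day window and no version based on maximum post-baseline values, and it makes no reference to baseline bilirubin. SAP Appendix A carries it as Listing 2.8.4.

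Four parts of the protocol decide when these values are seen:

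- **Schedule (Table 5).** On-treatment serum chemistry falls under the column "End of Weeks 4, 8, 12, 16, 20, and 24 and Then Q12W". The chemistry row is blank for Weeks 2, 6, 10 and 30.
- **Repeats (8.3.5 and 8.6).** Clinically significant abnormal results "should be repeated until the values return to normal or baseline", or until they are no longer judged clinically significant. Unscheduled results go on their own visit page in the eCRF.
- **Treatment interruption (6.7.2, Table 11).** For ALT or AST above 5.0 × ULN the guideline is "Interrupt piasclisib or matching placebo for up to 2 weeks (14 days) until the toxicity has resolved" to Grade 1 or lower.
- **Eligibility (5.2, criterion 6a).** A person with total bilirubin above 2.0 × ULN is normally excluded, but "the participant may enroll if the direct bilirubin is" below 2.0 × ULN.

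**The concern.** Transaminases and bilirubin need not be raised on the same day. If ALT or AST has dropped to 3 × ULN or lower by the time bilirubin passes 2 × ULN, no single visit satisfies the rule. The protocol makes this sequence plausible: scheduled chemistry is 4 and later 12 weeks apart, drug is interrupted above 5 × ULN, and a prompt repeat counts as a separate visit that the rule cannot pair with the draw that led to it.

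Comparative safety is a stated objective (Protocol 3, SAP 2.2). Protocol 2.6.1.3 cites fatal and/or serious hepatotoxicity in 16%–18% with idelalisib, another PI3K inhibitor, and ALT or AST of at least 5 × ULN is an adverse event of special interest (Protocol 9.5). Listing 2.8.4 is the only planned output named for combined liver injury, so an empty one is likely to be read as reassurance. A smaller issue runs the other way: a participant admitted under 6a with persistently raised total bilirubin would be listed on an ALT/AST rise alone, with no change in bilirubin.

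**Working it through.** The plan states no figure to reproduce. The check applies the rule literally to short hypothetical profiles, then sets it against the visit schedule.

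**Step 1: the rule applied.** Values are multiples of ULN, with ALP below 2 × ULN throughout.

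| Profile | First draw | Second draw | Does any visit meet all criteria? |
|---|---|---|---|
| A | Week 4: ALT 8, bilirubin 1.5 | Week 8: ALT 2.5, bilirubin 3 | No, not listed |
| B | Week 4: ALT 8, bilirubin 1.5 | Week 8: ALT 4, bilirubin 3 | Yes, Week 8, listed |
| C | Week 8: ALT 8, bilirubin 1.4 | One week later, unscheduled: ALT 2.9, bilirubin 3 | No, not listed |

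In B the recorded highs fall on different dates, yet the participant is listed. What matters is whether any one draw exceeds both thresholds with ALP below 2 × ULN. A and C fail because at the first draw bilirubin is still under 2 and at the second ALT is already under 3.

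**Step 2: are unscheduled draws excluded?** No. SAP 9.3.3 is not limited to scheduled visits, and Protocol Table 14 puts ALT, AST, ALP and both bilirubins in one chemistry panel. An unscheduled panel can qualify by itself. It cannot be joined to the draw before it.

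**Step 3: spacing of scheduled chemistry, using the Table 3 windows.**

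- Weeks 4 to 24: nominal gap 28 days with ±5 days at each end, so 28 − 10 = 18 to 28 + 10 = 38 days.
- Week 24 to Week 36: nominal 84 days with ±5 and ±7, so at least 84 − 12 = 72 days.
- Later extension visits: nominal 84 days with ±7 at each end, so at least 84 − 14 = 70 days.

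An illustrative 30-day window would therefore capture C (7 days) and A at its nominal 28 days, but not an A-type pair drawn 31 to 38 days apart. After Week 24 two consecutive scheduled extension draws are never within 30 days, so a window of that length works there only through unscheduled repeats. Covering every pair of consecutive scheduled draws up to Week 24 needs at least 38 days.

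**Step 4: do other outputs make the pairing?**

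- SAP 9.3.2 counts participants with abnormal ALT, AST and bilirubin by treatment group.
- The chemistry shift tables (3.3.2.2, 3.3.3.2) show the worst value for each test.
- Listings 2.8.2 and 2.8.3 show chemistry values and abnormal values.
- SAP 9.2.2 tabulates ALT and AST events of at least 5 × ULN, with time to onset and duration.
- Table 3.3.4.1 summarises liver chemistry elevations, but its shell is not in the documents.

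All of these show the elevations. None, as described, links ALT/AST to bilirubin within a participant over time.

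**The case against.** The strongest reply is that the affected group is narrow and the single elevations remain visible. Much of it stands.

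- **Peaks on different dates.** A reader might infer that any participant whose ALT/AST and bilirubin peaks differ in date is missed. Profile B shows otherwise.
- **Never detected.** A reader might infer that these participants disappear from the report. They do not: the elevations appear in the outputs in Step 4, and an ALT of 8 × ULN, as in A and C, meets the special-interest threshold and would be followed to resolution or stabilisation. What is absent is their identification as potential Hy's law cases.
- **Interruption.** Table 11 sets its transaminase trigger at 5.0 × ULN. Between 3 and 5 × ULN the interruption argument does not apply, though spacing and separate visit pages still do.
- **Repeats help too.** More draws also mean more chances for one to meet all criteria.
- **Exclusion 6a.** Over-inclusion is tolerable in a listing of potential events that goes to medical review, and direct bilirubin is collected. This supports a marker, not a claim that the rule is invalid.
- **Unseen shell.** Table 3.3.4.1 might pair maximum ALT/AST with maximum bilirubin. That cannot be confirmed or ruled out.

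The reply does not remove the gap: the one output meant to bring transaminases and bilirubin together does so only within a visit.

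**Conclusion.** The point holds in limited form. Participants who exceed the ALT/AST and bilirubin thresholds only at different visits are not captured in Listing 2.8.4, and the visible SAP text plans no window-based or maximum-post-baseline pairing.

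Its size cannot be given. It is tempting to say that one or two cases would be missed among the roughly 220 participants randomised to parsaclisib (440 / 2), but no document supplies a rate of combined elevations or of their timing. The 16%–18% belongs to idelalisib, and the common adverse events that Protocol 2.6.1.2 and 2.6.2.2 list for parsaclisib, alone and with ruxolitinib, include no hepatic event.

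The consequence is confined to one descriptive safety listing; no hypothesis test, error rate, power figure or interim rule changes. The conclusion assumes a literal reading of 9.3.3 and that the unseen table shell does not already do the pairing. It is worth changing because it is cheap and serves a stated comparative safety objective.

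**What to change.** Keep the same-visit listing and extend SAP 9.3.3 and Listing 2.8.4 as follows:

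1. Add participants with a post-baseline ALT or AST above 3 × ULN, with ALP below 2 × ULN at that draw, and total bilirubin above 2 × ULN within a prespecified window. Retaining the ALP condition avoids loosening the definition.
2. State the window length and whether it runs in both directions. Thirty days is one example, an assumption with no source in the documents; the spacing in Step 3 should inform the choice.
3. Use scheduled and unscheduled results.
4. Show ALP and direct bilirubin as columns, and mark participants whose baseline total bilirubin was already above 2 × ULN.
5. Distinguish same-visit from window-based entries, so that the current definition can still be read off.

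If the Table 3.3.4.1 shell already pairs maximum values, say so in 9.3.3. The change uses data already collected and alters no visit, test or treatment rule. It costs a sentence or two in the SAP, a small programming change and medical review of a few more participants, some of whom will not have drug-related liver injury.
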